Non-inferiority will be declared if the lower bound of the 2-sided 95% credible interval of the difference between the Test lens and the Control lens is greater than -5, i.e., $P(\beta_1 > -5) \geq 0.975$.

Vision Satisfaction in Bright Lighting

Vision satisfaction in bright lighting will be analyzed using a Bayesian multinomial model for ordinal data. The regression model will include sequence of lens wear, lens type, period and first order carryover effect. Clinical site and subject nested within clinical site will be included as random effects. Other subject characteristics such as age, gender, race and iris category will be included when appropriate.

The Model:

Let $y_{ijklm} = (y_{ijklm1}, y_{ijklm2}, y_{ijklm3}, y_{ijklm4}, y_{ijklm5})$ denote the rating for the m^{th} subject, from the l^{th} site, assigned to the i^{th} study lens in the j^{th} period using the k^{th} sequence. Possible values of y_{ijklm} are 1 if the subject rating of vision satisfaction in bright lighting are X and 0 otherwise (x=1 for Strongly Agree and X=5 for Strongly Disagree, respectively). The likelihood is constructed as follows:

$$y_{ijklm} \sim \text{Multinomial}(P_{ijklm1}, P_{ijklm2}, P_{ijklm3}, P_{ijklm4}, P_{ijklm5})$$

$$P_{ijklm1} = \gamma_{ijklm1}$$

$$P_{ijklmX} = \gamma_{ijklmX} - \gamma_{ijklm(X-1)} \quad 2 \leq n \leq 4$$

$$P_{ijklm5} = 1 - \sum_{x=1..4} P_{ijklmX}$$

$$\text{Logit}(\gamma_{ijklmX}) = \theta_n + \beta_1 \text{Lens}_{i[j,k]} + \beta_2 \text{Period}_{j1} + \beta_3 \text{Period}_{j2} + \beta_4 \text{Sequence}_k + \beta_5 \text{Carry}_{i[j,k]} + \gamma_l + \delta_{m(l)}$$

Where θ_n is the intercept for levels n=1,2,3,4, $P_{ijklm1} = \text{Pr}(\gamma_{ijklm1} = 1)$ with respect to the vision satisfaction in bright lighting item. We assume the random subject effects are independent identically distributed (i.i.d) as $\delta_{m(l)} \sim N(0, \sigma_{\text{subject}}^2)$ for subject m nested within clinical site l and

the random clinical site effects are i.i.d as $\gamma_l \sim N(0, \sigma_{site}^2)$ for $i=1,2$ (lens), $j=1, 2, 3$ (Period) $k=1, 2$ (Sequence) $l=1, \dots, 6$ (Site) $m=1, \dots, n_l$ (subject/site).

In this model, the lens I will be determined by the period j and sequence k , therefore i is denoted as a function of j and k . We define $Lens_i=0$ for the Control lens and $Lens_i=1$ for the Test lens. The cumulative odds ratio for having higher rating can be written as $OR=e^{\beta_1}$.

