For each item k, the superiority will be declared if the lower bound of the 2-sided 95% credible interval of OR_k is greater than 1: $Pr(OR_k > 1 | \mathbf{y}) \geq .975$.

Outdoor Glare Reduction

Outdoor Glare reduction consists of 4 individual questionnaire items.

1. Ability to see comfortably in bright sunlight
2. Reduction in glare caused by bright sunlight
3. Reduction of squinting in bright sunlight
4. Reduction of eyestrain in bright sunlight

All outdoor glare items are assessed using the same ordinal scale (1=Excellent ... 5=Poor). Outdoor Glare reduction items will be analyzed separately using a Bayesian multinomial model for ordinal data adjusting for baseline. The regression model will include sequence of lens wear, lens type, period and first order carryover effect. Clinical site and subject nested within clinical site will be included as random effects. Other subject characteristics such as age, gender, race and iris category will be included when appropriate.

The Model:

Let $y_{ijklm} = (y_{ijklm1}, y_{ijklm2}, y_{ijklm3}, y_{ijklm4}, y_{ijklm5})$ denote the rating for the m^{th} subject, from the l^{th} site, assigned to the i^{th} study lens in the j^{th} period using the k^{th} sequence. Possible values of y_{ijklm} are 1 if the subject rating of outdoor glare items are X and 0 otherwise (x=1 for Excellent and X=5 for Poor, respectively). The likelihood is constructed as follows:

$$y_{ijklm} \sim \text{Multinomial}(P_{ijklm1}, P_{ijklm2}, P_{ijklm3}, P_{ijklm4}, P_{ijklm5})$$

$$P_{ijklm1} = \gamma_{ijklm1}$$

$$P_{ijklmX} = \gamma_{ijklmX} - \gamma_{ijklm(X-1)} \quad 2 \leq n \leq 4$$

$$P_{ijklm5} = 1 - \sum_{x=1..4} P_{ijklmX}$$

$$\text{Logit}(\gamma_{ijklm}) = \theta_n + \beta_1 \text{Lens}_{i[j,k]} + \beta_2 \text{Period}_{j1} + \beta_3 \text{Period}_{j2} + \beta_4 \text{Sequence}_k + \beta_5 \text{Carry}_{i[j,k]} + \gamma_l + \delta_{m(l)}$$

Where θ_n is the intercept for levels n=1,2,3,4, $P_{ijklm1} = \Pr(\gamma_{ijklm1} = 1)$ with respect to outdoor glare preference. We assume the random subject effects are independent identically distributed (i.i.d) as $\delta_{m(l)} \sim N(0, \sigma_{\text{subject}/\text{site}}^2)$ for subject m nested within clinical site l and the random clinical site effects are i.i.d as $\gamma_l \sim N(0, \sigma_{\text{site}}^2)$ for i=1,2 (lens), j=1, 2, 3 (Period) k=1, 2 (Sequence) l=1, ... 5 (Site) m=1, ... n_l (subject/site).

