In this model, the lens I will be determined by the period j and sequence k, therefore i is denoted as a function of j and k. We define $\text{Lens}_i=0$ for the Control lens and $\text{Lens}_i=1$ for the Test lens. The odds ratio for having higher rating can be written as $OR = e^{-\beta_1}$.

Independent vague $N(0, 1000)$ priors for the regression coefficients β_i i=1,...5. For θ_n , we are considering the following priors

$$\begin{aligned}\pi_0(\theta_1) &\sim N(0, 100) \\ \pi_0(\theta_2 | \theta_1) &\sim N(0, 100) I(\theta > 0) \\ \pi_0(\theta_3 | \theta_2) &\sim N(0, 100) I(\theta > 0) \\ \pi_0(\theta_4 | \theta_3) &\sim N(0, 100) I(\theta > 0)\end{aligned}$$

For the variance of random effects independent vague normal priors will also be used; $\sigma_p^2 \sim \text{inverse-gamma}(0.001, 0.001)$ and $\sigma_s^2 \sim \text{inverse-gamma}(0.001, 0.001)$. The Metropolis sample algorithm as implemented in the SAS/Stat MCMC Procedure will be used to estimate the posterior distributions of the unknown parameters. Inferences will be made based on the posterior credible interval for the relevant parameters.

Hypothesis Testing

The null and alternative hypotheses for superiority are as follows:

$$\begin{aligned}H_0 \quad OR &\leq 1 \\ H_A \quad OR &> 1\end{aligned}$$

Where OR represent the cumulative odds ratio of having higher rating of the Test lens compared to the Control lens where the OR is calculated as $OR = e^{-\beta_1}$. Superiority will be declared if the lower bound of the 2-sided 95% credible confidence interval is above 1, i.e.

$$P(OR = e^{-\beta_1} > 1 | y) = 0.975.$$

Indoor Glare Reduction

Indoor Glare reduction consists of 4 individual questionnaire items:

1. Reduction in squinting while using computer screens or digital devices
2. Reduction in glare from the computer screen or digital devices
3. Reduction in glare caused by bright indoor lights
4. Reduction in glare caused by bright light coming through the window

Each item will be analyzed individually and tested in the exact same manner as the Outdoor Glare Reduction Items described above.

Driving Measures

Driving measure consists of two individual questionnaire items:

1. Reduction in glare while driving during the day
2. Reduction in glare while driving during the night

Each item will be analyzed individually in the exact same manner as the Outdoor Glare Reduction Items described above. However, the hypothesis test will be as follows:

Hypothesis Testing

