The null and alternative hypotheses for superiority are as follows:

$$\begin{aligned} H_0 & OR \leq 0.67 \\ H_A & OR > 0.67 \end{aligned}$$

Where OR represent the cumulative odds ratio of having higher rating of the Test lens compared to the Control lens. Non-inferiority will be declared if the lower bound of the 2-sided 95% credible confidence interval is above 0.67, i.e. $P(OR=e^{-\beta_1}>0.67|y)=0.975$. Superiority will be declared if the lower bound of the 2-sided 95% credible interval is above 1, i.e. $P(OR=e^{-\beta_1}> 1|y)=0.975$. Superiority will only be tested in the event that non-inferiority is established.

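### SAP 11.3 inverts the odds ratio for the outdoor, indoor and driving glare items, so Test can be declared superior only when it is rated worse ('Other' endpoints only)

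*SAP*

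**What the plan says.** SAP section 11.3 (Outdoor Glare Reduction) builds the model in four steps:

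- Scale: "All outdoor glare items are assessed using the same ordinal scale (1=Excellent ... 5=Poor"). The likelihood keeps that numbering, with X=1 for Excellent and X=5 for Poor.
- Cumulation: the first category probability equals γ1, and each later one is γX minus γ(X−1). So γX is the probability of a rating of X or better.
- Predictor: logit(γ) equals a threshold plus β1 times Lens, plus period, sequence, carryover and random terms. The coding is "We define $\text{Lens}_i=0$ for the Control lens and $\text{Lens}_i=1$ for the Test lens".
- Odds ratio: "The odds ratio for having higher rating can be written as $OR = e^{-\beta_1" (exp(−β1)), with superiority if the lower 95% credible bound exceeds 1.

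The four indoor items take over the outdoor test by reference. The two driving items repeat the negative exponent in both rules: "Non-inferiority will be declared if the lower bound of the 2-sided 95% credible confidence interval is above 0.67, i.e. $P(OR=e^{-\beta_1}>0.67|y)=0.975" and "Superiority will be declared if the lower bound of the 2-sided 95% credible interval is above 1, i.e. $P(OR=e^{-\beta_1}> 1|y)=0.975".

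For the primary bright-lighting item, section 11.1 has the same linear predictor with the best category at X=1, but says "The cumulative odds ratio for having higher rating can be written as $OR=e^{\beta_1" (exp(+β1)). Section 11.2 applies that method to vision indoors, which is rated from Excellent to Poor like the glare items.

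Section 5.3 hypothesises superiority of Test on at least 2 of 4 outdoor and 2 of 4 indoor measures, and non-inferiority on both driving items.

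**The concern.** The sign of the exponent does not match the model printed above it. A programmer who follows section 11.3 literally would code a decision rule that rewards a worse Test lens and blocks a better one. Protocol 14.7 foresees only descriptive summaries and optional exploratory analysis for these items, but SAP section 1 says the SAP prevails and the SAP gives formal pass rules.

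The historical counts in the documents favour Test, so the likelier harm is a missed benefit and a failed driving non-inferiority test. A false claim of superiority is possible but less likely.

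Two smaller points arise nearby. The threshold priors in 11.3 do not order the thresholds. And the visual acuity and CLUE equations in 11.1 do not say which period's lens the carryover term refers to.

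**Working it through.** The documents give no power or effect figure for the glare items, so there is none to reproduce.

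**1. Direction of β1.** Under the printed model, logit P(X or better | Test) − logit P(X or better | Control) = +β1, so the odds ratio for a better rating is exp(β1). As an example, take the Control counts for vision indoors in SAP Table 10, where P(Excellent) = 80/182 = 0.440.

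| β1 | P(Excellent) on Test | exp(β1) | printed exp(−β1) |
|---|---|---|---|
| +0.5 | 0.564 (better) | 1.65 | 0.61 |
| −0.5 | 0.322 (worse) | 0.61 | 1.65 |

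**2. Can another reading of 'higher rating' rescue it?** If higher means better, the exponent is wrong. If it means a larger category number, exp(−β1) is a correct odds ratio for a rating nearer Poor, but a value above 1 is then called superior. Both readings reverse the decision.

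**3. Driving non-inferiority.** exp(−β1) > 0.67 is the same as exp(β1) < 1/0.67 = 1.49. That caps how much better Test may be and does not exclude a worse Test lens.

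**4. Fit to counts in the documents.** These are proportional-odds fits with lens only and rows treated as independent. Neither item is itself affected.

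| Item (Test; Control, best to worst) | β1 (SE) | exp(β1), 95% CI | exp(−β1), 95% CI |
|---|---|---|---|
| Vision indoors, SAP Table 10 (100/55/23/3/0; 80/62/30/7/3) | 0.485 (0.200) | 1.62 (1.10–2.40) | 0.62 (0.42–0.91) |
| Bright light, Protocol Table 9 (72/129/24/17/0; 51/130/21/33/7) | 0.521 (0.175) | 1.68 (1.19–2.37) | 0.59 (0.42–0.84) |

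In both, the lower bound of the inverted ratio (0.42) lies below 1 and below 0.67, so a better-rated Test lens would fail both rules.

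**5. Chance of passing, per item, 105 completers.** Corrected rule: Φ((log OR − log threshold)/SE − 1.96). Printed rule: the same with −log OR. The SE of β1 is assumed to be 0.22 (range 0.15–0.30 in brackets). The true ORs are assumptions, because the documents give no glare or driving counts.

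| True better-rating OR | Rule | As printed | Corrected |
|---|---|---|---|
| 1.62 | superiority | <0.1% | 59% (36–90%) |
| 1.62 | driving non-inferiority | 1.0% (0.6–1.3%) | 98.0% (84% to >99.9%) |
| 1.0 | driving non-inferiority | 44% (27–76%) | 44% (27–76%) |
| 0.67 | driving non-inferiority | 95% (76% to >99.9%) | 2.5% |
| 0.50 | superiority | 88% (64% to >99%) | <0.1% |

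First row: log 1.62 = 0.482; 0.482/0.22 − 1.96 = 0.23; Φ(0.23) = 59%.

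A simulation of 300 trials per scenario (three periods, with lens, period, sequence and carryover effects) agrees. With Test better by an OR of 1.62, the printed rule declared superiority in 0% of trials and the corrected rule in 56%. With Test worse by the same factor, the figures were 63% and 0%.

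**6. Threshold priors.** Section 11.3 uses "\pi_0(\theta_2 | \theta_1) &\sim N(0, 100) I(\theta > 0"), and the same form for thresholds 3 and 4. Being positive does not put them in order. The protocol printed this form for bright lighting. SAP 11.1 replaced it there with bounds at the preceding threshold, and 11.3 was left unchanged.

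**7. Carryover in SAP 11.1 (conditional).** Let b, s and c be the lens, sequence and carryover effects. Take the Test/Control/Control minus Control/Test/Test difference in mean by period.

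| Period | preceding-lens carry, printed minus in period 3 | preceding-lens carry, plus in period 3 |
|---|---|---|
| 1 | b + s | b + s |
| 2 | −b + s + c | −b + s + c |
| 3 | −b + s + c | −b + s − c |

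In the middle column two equations coincide, leaving three unknowns for two equations (design rank 5 of 6), so the lens effect is not identified. The right-hand column has rank 6. Carry defined by the first lens worn, with the printed minus, also has rank 6 and differs from the right-hand column only by a period-3 constant. The protocol's own equations, with a minus on Sequence in period 2, have rank 6 under both readings.

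With the SAP's comfort covariance matrix and n=105, the posterior SD of b is 1.98 CLUE points in the sound cases, against a margin of 5. In the unidentified case it is 13.0, set by the prior (N(0, 1000) read as a variance).

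**The case against.** The best counter-argument is that the sign change was deliberate. The raw scales run in opposite directions: SAP 4.1 codes bright-lighting satisfaction from 1 = Strongly Disagree to 5 = Strongly Agree, while the glare items run from 1 = Excellent to 5 = Poor. If the program models raw codes towards higher values, exp(β1) for bright lighting and exp(−β1) for the glare items could both be right, and the misprint would be in the shared model block. Changing the exponent alone might then break a correct program. That is possible, but it is not what the SAP prints: 11.3 gives X=1 for Excellent and a plus sign, and 11.2 applies exp(β1) to an Excellent-to-Poor item. What stands is the need to check the code. That check should cover the recoding of bright lighting, since 11.1 puts Strongly Agree at X=1 and states no recoding step.

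Other objections stand in part:

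- The items are 'Other' endpoints, and the frequency tables by lens in SAP 8.2 would contradict a reversed result. This limits the consequence but does not repair the rule.
- The rule can never declare Control the winner; it can only declare Test wrongly, or fail to declare it.
- The SE of 0.22 is at the low end. Calculated from the model with a subject random intercept (SD 0 to 2.5), it is 0.222 to 0.278. At 0.278 the corrected superiority chance at OR 1.62 is 41%, not 59%. The sign result does not depend on this.
- Disordered thresholds give invalid category probabilities wherever there are data, so the prior defect may have little effect in practice.
- The carryover point is a missing definition, not a demonstrated error.

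**Conclusion.** The concern holds. Under the model printed in SAP 11.3, exp(−β1) is the odds ratio for a worse rating, and the rules for 4 outdoor, 4 indoor and 2 driving items are reversed. This is exact algebra and needs no assumption. The pass chances rest on an assumed SE and assumed true odds ratios, and the fits in step 4 use neighbouring items.

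The primary objective does not depend on these items (SAP 5.1), and the primary and secondary ordinal rules have the right sign for the models they print. The program is not in the documents and may already be correct. The point should be fixed, but it does not threaten the main conclusions. The carryover clarification, if left open, could at worst produce a visible failure to conclude on visual acuity or CLUE, not a false claim.

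**What to change.** In SAP 11.3, replace exp(−β1) with exp(+β1) in the outdoor definition and superiority rule and in both driving rules; the indoor items follow by reference. An equivalent correction is to keep exp(−β1) and either enter Lens with a minus sign or cumulate from Poor. Whichever is chosen, predictor, category order and odds ratio must agree, and the program must be checked against them, including the category order used for bright lighting.

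In the same section, replace the positivity bounds on thresholds 2 to 4 with the ordered bounds already used in 11.1.

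Separately, for the visual acuity and CLUE models in 11.1 and 11.2, state one matching pair of carryover definition and sign. One option is the preceding lens (0 in period 1) with a plus in periods 2 and 3. Another is the first lens worn, with the signs as printed.

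The cost is SAP wording and a code check; nothing changes in the conduct of the trial.

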Independent vague $N(0, 1000)$ priors for the regression coefficients β_i $i=1, \dots, 5$. For θ_n , we are considering the following priors

$$\begin{aligned}\pi_0(\theta_1) &\sim N(0, 100) \\ \pi_0(\theta_2 | \theta_1) &\sim N(0, 100) I(\theta > \theta_1) \\ \pi_0(\theta_3 | \theta_2) &\sim N(0, 100) I(\theta > \theta_2) \\ \pi_0(\theta_4 | \theta_3) &\sim N(0, 100) I(\theta > \theta_3)\end{aligned}$$

For the variance of random effects independent vague normal priors will also be used; $\sigma_p^2 \sim \text{inverse-gamma}(0.001, 0.001)$ and $\sigma_s^2 \sim \text{inverse-gamma}(0.001, 0.001)$. The Metropolis sample algorithm as implemented in the SAS/Stat MCMC Procedure will be used to estimate the posterior distributions of the unknown parameters. Inferences will be made based on the posterior credible interval for the relevant parameters.

Hypothesis Testing

The null and alternative hypotheses for superiority are as follows:

$$\begin{aligned}H_0 \quad OR &\leq 0.67 \\ H_A \quad OR &> 0.67\end{aligned}$$

Where OR represent the cumulative odds ratio of having higher rating of the Test lens compared to the Control lens. Non-inferiority will be declared if the lower bound of the 2-sided 95% credible confidence interval is above 0.67, i.e. $P(OR=e^{\beta_1} > 0.67 | y) = 0.975$.

Primary Safety Analysis:

Lens Fit Acceptance

Lens fit acceptance will be analyzed using a Bayesian Logistic regression random-effects model to estimate the proportion of subjects' eyes wearing the Test lens having acceptable lens fitting. The regression model will include period, sequence of lens wear and first order carryover effect as fixed effects. Site and subject will be included in the model as random effects.

Let $y_{ijklm}=1$ if an acceptable lens fit is observed for eyes wearing the Test lens only and $y_{ijklm}=0$ otherwise for the m^{th} subject, from the l^{th} site, for the i^{th} eye in the j^{th} period using the k^{th} sequence.

$$y_{ijklm} \sim \text{Binary} (p_{ijklm})$$

$$p_{ijklm} = \frac{\exp(\mu_{ijklm})}{1 + \exp(\mu_{ijklm})}$$

$$\mu_{ijklm} = \beta_0 + \beta_1 \text{Lens}_{i[j,k]} + \beta_3 \text{period}_{j1} + \beta_4 \text{period}_{j2} + \beta_5 \text{sequence}_k + \beta_6 \text{Carry1}_{i[j,k]} + \gamma_1 + \delta_{m(l)} + \alpha_{j(m(l))}$$

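### SAP 11.3 truncates the ordinal cutpoints at zero instead of at the previous cutpoint, so the prior does not order them and can bias the lens effect on ten exploratory items

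*SAP*

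**What the plan says.** SAP 11.3 (Outdoor Glare Reduction) sets up a cumulative-logit model in which θₙ "is the intercept for levels n=1,2,3,4". Ratings are coded "x=1 for Excellent and X=5 for Poor, respectively", so the second cumulative probability is that of Excellent or Very Good. The lens reference is Control: "We define $\text{Lens}_i=0$ for the Control lens". The prior on each of θ₂, θ₃ and θ₄ is "N(0, 100) I(\theta > 0", that is, truncated at zero.

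The indoor items reuse all of this: "Each item will be analyzed individually and tested in the exact same manner as the Outdoor Glare Reduction Items described above". The driving items reuse the model with a different test. By the lists in 11.3 this covers 4 + 4 + 2 = 10 items.

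SAP 11.1 has the same cumulative form for vision satisfaction in bright lighting, but its prior for θ₂ is "N(0, 100) I(\theta > \theta_1", and θ₃ and θ₄ are chained in the same way. Protocol 14.5 prints the zero truncation for the bright-lighting item. The SAP, which takes precedence, changed it there but not in 11.3.

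**The concern.** Cutpoints of a cumulative-logit model must increase. A truncation at the previous cutpoint secures that; a truncation at zero does not, and it adds a restriction on the level of the ratings that nobody appears to have intended. If the data contradict that restriction, the other terms in the model, including the lens effect, have to take up the misfit. SAP 5.3 attaches formal claims to these items: superiority on at least 2 of 4 outdoor and at least 2 of 4 indoor items, and non-inferiority on both driving items at an odds-ratio margin of 0.67.

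**Working it through.** The plan states no power or error rate for these items, so there is no figure to reproduce.

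**1. Ordering.** Under the printed prior, θ₂, θ₃ and θ₄ are independent half-normals, and θ₁ is N(0, 100) without restriction. Category probabilities are differences of adjacent cumulative probabilities, so any reversed pair gives a negative one. The prior probability that all four are in order is ½ × 1/3! (θ₁ negative) + ½ × 1/4! (θ₁ positive) = 1/12 + 1/48 = 5/48, about 10%. Observed ratings in every category would push the fit towards valid orderings, but the prior does not secure them.

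**2. Level.** In the reference cell (Control, reference period, Sequence 0, no carryover, zero random effects), P(Excellent or Very Good) = expit(θ₂). With θ₂ > 0 this exceeds expit(0) = 0.50.

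**3. Where a forced shift goes.** There are six sequence-by-period cells and six mean parameters (level, lens, two periods, sequence, carryover), with rank 6. A forced rise in the level must therefore distort the other terms. In a linear approximation β₁ moves by −0.40, −0.33 or −0.26 per logit of forced shift at within-subject correlation 0, 0.2 or 0.4.

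**4. Simulation.** Inputs from the documents: the 11.3 model form, its priors, and 105 completers (SAP 8.4). Assumptions: subject SD 1.0, site SD 0.3, no true period, sequence or carryover effects, period 3 as reference, and the Control rates shown (at zero random effects). Six sites were used, as in SAP 11.1; 11.3 indexes five. There were 60 trials per row, each fitted under both truncations. The Monte Carlo SE of a mean is about 0.03.

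| Control, Very Good or better | True β₁ | Mean β₁, 11.1 / 11.3 truncation | 95% coverage, 11.1 / 11.3 | Median site SD, 11.1 / 11.3 |
|---|---|---|---|---|
| 78% | 0 | −0.02 / −0.01 | 0.97 / 0.97 | 0.21 / 0.21 |
| 50% | 0 | 0.02 / −0.06 | 0.90 / 0.92 | 0.25 / 0.27 |
| 40% | 0 | 0.00 / −0.15 | 0.95 / 0.88 | 0.22 / 0.29 |
| 30% | 0 | 0.01 / −0.18 | 0.92 / 0.88 | 0.18 / 0.46 |
| 20% | 0 | 0.01 / −0.15 | 0.95 / 0.87 | 0.20 / 1.21 |
| 30% | ln 1.5 = 0.405 | 0.37 / 0.19 | 0.95 / 0.85 | 0.20 / 0.40 |

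Steps 3 and 4 agree. In the 30% null row the mean θ₂ rises from −0.89 to 0.18, a shift of 1.07. The mean site effect takes up 0.43, leaving 0.64. Then 0.64 × 0.26 to 0.33 gives 0.17 to 0.21, against a simulated shift of 0.19.

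**5. Direction.** With 1 as the best category, a positive β₁ raises the probability of better ratings. SAP 11.1 reports exp(β₁); SAP 11.3 reports exp(−β₁) in the same form. In the 30% null row exp(−β₁) = exp(0.184) = 1.20 and exp(β₁) = 0.83, where both should be 1.0.

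**6. Documentary anchor.** The only item on the Excellent-to-Poor scale with a historical distribution is vision indoors (SAP Table 10). Control is (80 + 62)/182 = 78.0% Very Good or better.

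**The case against.** The strongest reply is that the restriction may never bind. The one tabulated item on this scale has Control at 78%, where the check finds no bias. That stands as a limit. It does not settle the matter, because general vision indoors is a different and probably easier question than glare or squinting in bright sunlight, and the documents give no distribution for those.

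Second, zero truncation would be right if θ₂ to θ₄ were positive increments. But 11.3 defines them as the level intercepts and never as increments, so either the prior or the definition has to change.

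Third, the stakes are limited. These are Other hypotheses under an exploratory objective. The bright-lighting item has the chained truncation in 11.1, and the secondary vision-indoors item follows that model (SAP 11.2). This stands in full.

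Two stronger readings are tempting and are not supported. A reader might infer that real benefits of the Test lens would be missed. That follows only if the odds ratio is exp(β₁); with exp(−β₁), as 11.3 prints it, the same bias inflates the Test odds ratio. A reader might also infer that at least half of all Control ratings are forced to be Very Good or better. The floor applies to the reference cell at zero random effects, and site effects can absorb part of it, as the inflated site SD shows.

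**Conclusion.** The prior in SAP 11.3 is wrong for the parameters as that section defines them, and it contradicts SAP 11.1. Two consequences need no data: the cutpoints are not ordered, and the reference-cell probability of Excellent or Very Good is held above 50%.

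The effect on inference is conditional. If Control ratings on an item fall below about 50% Very Good or better, β₁ is biased downward by roughly 0.15 to 0.2 logits, coverage is 0.85 to 0.88, and site variance is inflated. At exactly 50% the bias is small (−0.06), and at 78% it is absent. These sizes rest on the assumed SDs, category spacing and site number, and with 60 trials a coverage of 0.88 has a standard error of √(0.88 × 0.12/60) = 0.04. Which lens benefits cannot be said until the sign of the odds ratio is settled. No primary or secondary conclusion is affected.

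**What to change.** In SAP 11.3 replace the three zero truncations by θ > θ₁ for θ₂, θ > θ₂ for θ₃ and θ > θ₃ for θ₄, as in 11.1. Alternatively, state that θ₂ to θ₄ are positive increments and write the logit accordingly. At the same time reconcile exp(−β₁) in 11.3 with exp(β₁) in 11.1, so that one stated direction means a better rating on Test. Check that the PROC MCMC code for all ten items matches.

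The cost is three symbols, one sign decision and a code check. It is best done before database lock, because a change made after seeing whether the restriction binds would be post hoc.
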